1. OBJECTIVES

1.1. Primary Objective

- To determine whether the addition of the BioBridge scaffold to vascularized lymph node transfer will improve the outcome of surgical treatment of secondary arm lymphedema resulting from treatment of breast cancer. Primary endpoint is the post-surgical % change in excess limb volume, measured at 12 months following the surgical procedure. Intervention participants will be consented for safety follow-up for up to 36 months.

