VLNT, 2 groups; one with BioBridge scaffold (intervention group), one VLNT only (control group), will occur between S3 and T1 visits.

T1 (3 months following surgery): physical exam, measurements, LymQoL survey, medication and symptom/AE review, VS, weight.

T2 (6 months following surgery): physical exam, measurements, LymQoL survey, medication and symptom/AE review, VS, weight

T3 (9 months following surgery): physical exam, measurements, LymQoL survey, medication and symptom/AE review, VS, weight.

T4 (12 months following surgery): physical exam, measurements, LymQoL survey, medication and symptom/AE review, VS, weight, skin punch biopsy (optional for control group), research labs. No compression garment wear x 10 days.

T5 (10 days after T4 visit): measurements, LymQoL survey, medication and symptom/AE review, VS, weight, stitch removal, LSG

T6 (2 years following surgery, BioBridge participants/intervention group): physical exam, medication and symptom/AE review, VS, weight.

T7 (3 years following surgery, BioBridge participants/intervention group): physical exam, medication and symptom/AE review, VS, weight.

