9. STUDY CALENDAR

	Pre-Study	S1	S2	S3	Surgery: VLNT with BioBridge (BB) Or VLNT only	T1 Mo. 3	T2 Mo. 6	T3 Mo. 9	T4 Mo. 12	T5 D-10 FU	T6 2-yr FU (BB group Only)	T7 3-yr FU (BB group Only)
Investigational Device (BioBridge Matrix)					X	X	X	X	X	X	X	X
Informed consent	X											
Demographics	X											
Medical history	X											
Concurrent meds	X	X	X	X		X	X	X	X	X	X	X
Physical exam	X	X		X		X	X	X	X	X	X	X
Vital signs	X	X	X	X		X	X	X	X	X	X	X
Height	X											
Weight	X	X	X	X		X	X	X	X	X	X	X
Performance status (ECOG)	X	X				X	X	X	X	X	X	X
CBC w/diff, platelets	X											
Serum chemistry	X											
EKG (as indicated)	X											
Adverse event evaluation		X	X	X		X	X	X	X	X	X	X
Measurements (BIS, VM, calipers)		X	X	X		X	X	X	X	X		
LymQoL survey		X	X			X	X	X	X	X		
Skin punch biopsy (optional for control group)			X						X			
Research labs			X						X			
Radiologic evaluation (Lymphoscintigraphy)				X						X *		
Pregnancy test (as indicated)												

* BioBridge Matrix recipients only.

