12.4 Primary Analysis

Limb circumference of the affected and unaffected limbs of each participant will be measured for calculation of the volume of the arm through the truncated cone formula.²³ Circumferential measurements of each limb will be obtained with a low stretch gauged tape measure applied at specified intervals of 4 cm (starting from the 3rd metacarpal head) along the axis of the arm, beginning at the wrist. Anatomic landmarks are recorded to facilitate reproducibility between pre- and post-surgical measurements. This method is inexpensive, reproducible, and easily applied. These measurements will be performed at initial evaluation and at each scheduled follow-up visit. The pre-surgical baseline volume for each limb will be defined as the average of the two measurements obtained on study day S1 and study day S2. For quantitative analysis, the excess volume of the limb is defined as the arithmetical difference between the affected

limb (L_{pre}) and the contralateral normal limb (C_{pre}) and the % excess volume at the beginning of the study is defined by:

$$100\% * [(L_{pre} - C_{pre})/C_{pre}].$$

The primary outcome is defined the post-surgical % change in excess limb volume:

$$100 * \{1 - [(L_{post} - C_{post})/(L_{pre} - C_{pre})]\}$$

Analysis Population

Participants are randomized into 1 of 2 arms, the intervention arm (VLNT with BioBridge) or control arm (VLNT-only). The primary analysis will include all participants who have completed all required study visits. However, for participants who do not complete the study, their data will be censored and analyzed with the current population. Treatment summary and adverse event data will also be provided for each treatment category separately.

Efficacy and safety analyses will be performed on all participants who have undergone VLNT (with or without BioBridge). The primary analysis will include all participants who have completed all required study visits and procedures. However participants who do not complete the study will be censored and their data will be analyzed, along with ongoing participants. Data including adverse event data will be captured for each treatment category separately.

Analysis Plan

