The final analysis will be undertaken after the final enrolled participant completes all planned study events. At that time, the data will be unblinded and the analyses will be undertaken as described above. There will be multiple analysis populations. The primary analysis will use all subjects enrolled and assigned to treatment, categorized by their planned treatment. A sensitivity analysis will use the set of subjects enrolled and treatment-assigned in the study who completed the study protocol, categorized according to treatment actually received.

Generalized linear mixed effects models are maximum likelihood based methods that are ideal for handling missing outcome data. More specifically, in prospective clinical trials such as the one proposed, a major concern is loss to follow up. The model we have proposed accommodates anticipated loss to follow up and allows us to analyze subjects treated in the study even if they are lost to follow up, ie, if a subject is lost to follow up, the subject is included in the analysis if at least one post-baseline value is recorded prior to loss to follow up). This model relies on a flexible assumption about the missing data, namely that the missing values are missing at random (ie, that missingness is related to observed values only such as baseline volume values and treatment arm). Given the nature of the data generated, we believe this to be a reasonable assumption.

To allow for the possibility that the response variable may not have a linear relationship with the time variable, we will treat time as a categorical variable to allow time to have a non-linear relationship with the response. The categorical time variable can take on values of 3, 6, 9, or

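### Adverse events are reviewed to 36 months in the BioBridge arm but only to T5 (12 months + 10 days) in controls, and the by-arm summary in 12.4 sets no common window

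*Combined protocol and SAP*

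**What the plan says.** **Collection.** Both arms have adverse event review at T1 to T5. The last of these in Section 4 (Study Visits) is "T5 (10 days after T4 visit): measurements, LymQoL survey, medication and symptom/AE review, VS, weight, stitch removal, LSG". After that the schedule is for one arm only: "T6 (2 years following surgery, BioBridge participants/intervention group): physical exam, medication and symptom/AE review, VS, weight" and "T7 (3 years following surgery, BioBridge participants/intervention group): physical exam, medication and symptom/AE review, VS, weight". The calendar in Section 9 agrees: the adverse event row is marked at T6 and T7, and both columns are restricted to BioBridge recipients ("T7 3-yr FU (BB group Only"). Section 1.1 says the same of consent: "Intervention participants will be consented for safety follow-up for up to 36 months".

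**Analysis.** Section 12.4 (Analysis Population) defines who is included: "Efficacy and safety analyses will be performed on all participants who have undergone VLNT (with or without BioBridge"). It then says: "Treatment summary and adverse event data will also be provided for each treatment category separately". On timing, 12.4 (Analysis Plan) says: "The final analysis will be undertaken after the final enrolled participant completes all planned study events". Section 12.2 plans no interim analysis.

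The documents do not set a common observation window for adverse events, a time-to-event method, or separate reporting of events after T5.

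**The concern.** The planned events include T7, so when the only by-arm summary is made the database will hold BioBridge events to month 36 and control events to about month 12.3. A summary by arm with no window would use all of them. The percentage of participants with at least one event can only rise with longer observation, so two arms with identical risk would be shown with different percentages, to the disadvantage of the device.

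The 12 controls are the trial's only randomised means of separating harm from the device from harm from the node-transfer operation. Because the trial is open-label, a window chosen after the events are known would also be open to criticism. It is better fixed in advance.

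**Working it through.** **The plan's own figures.** The documents give no adverse event rate for years 1 to 3, so there is no safety figure to reproduce. The one computed design figure is the detectable difference of ±20% in 12.6.2 (48 v 12, SD 19%, alpha 0.05, power 0.9). It reproduces: SE = 19 × √(1/12 + 1/48) = 6.13, and (1.960 + 1.282) × 6.13 = 19.9. It has no bearing on this point.

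**Observation per participant.** BioBridge: 36 months (1.1, T7). Control: 12 + 10/30.44 = 12.33 months (T5). Ratio 36/12.33 = 2.9.

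**Model with no device effect.** Let p be the 12-month risk, the same in both arms (an assumption). Let w be the share of the 36-month cumulative hazard that falls in the first 12 months (also an assumption). Then

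- control percentage at 12 months = p
- BioBridge percentage at 36 months = 1 − (1 − p)^(1/w)

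A constant hazard is w = 1/3, which gives 1 − (1 − p)³.

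*Constant hazard, varying p:*

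| p (control, 12 months) | BioBridge, 36 months | Ratio |
|---|---|---|
| 5% | 14.3% | 2.85 |
| 10% | 27.1% | 2.71 |
| 20% | 48.8% | 2.44 |
| 30% | 65.7% | 2.19 |

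At p = 20% the expected counts are 48 × 0.488 = 23.4 and 12 × 0.20 = 2.4. Counting controls to T5 instead of month 12 gives 20.5% v 48.8%, ratio 2.38.

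*p = 20%, varying w.* The last two columns are exact binomial probabilities for 48 v 12 participants; ties make up the rest.

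| Share of hazard in year 1 | BioBridge, 36 months | Ratio | P(BioBridge % higher) | P(control % higher) |
|---|---|---|---|---|
| 1/3 (constant) | 48.8% | 2.44 | 97% | 2% |
| 50% | 36.0% | 1.80 | 86% | 11% |
| 70% | 27.3% | 1.36 | 69% | 26% |
| 90% | 22.0% | 1.10 | 55% | 39% |
| 100% | 20.0% | 1.00 | 49% | 45% |

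**Incomplete follow-up.** Suppose accrual is uniform over 48 months (12.6.1) and follow-up stops at 72 months (3.5). Participants entering in the first 36 of the 48 months (75%) reach month 36; the rest average 30 months. Mean follow-up is 0.75 × 36 + 0.25 × 30 = 34.5 months. The constant-hazard figure at p = 20% falls only from 48.8% to 47.3%.

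**With a common window.** If both arms are summarised over the same period, the expected difference with no device effect is 0 at every p and w. At p = 20% the chance that BioBridge shows the higher percentage is 49%, and that control does, 45%.

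**Why a rate per patient-year does not solve it.** With no device effect, the ratio of event rates (36-month BioBridge over 12-month control) is 1/(3w): 1.00 at w = 1/3, but 0.67, 0.48 and 0.37 at w = 50%, 70% and 90%. Early surgical events divided by a long quiet follow-up would make the device look protective.

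**The case against.** The case on the other side has several parts.

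- **No comparison is specified.** Section 12.4 provides data by arm; no test, risk ratio or safety hypothesis is planned. This stands: the summary is descriptive, and the ratios above are what a reader would form from the table. But arms summarised side by side will be compared.
- **Month 12 is called study end** in 10.1.2 and 10.2.2, and 1.1 describes the longer period as safety follow-up, so T6 and T7 could be read as a single-arm extension. That is a reasonable intention, but those sections define efficacy measurements and consent. They do not bind the adverse event summary.
- **Most named complications are early.** The post-operative complications in 4.1 (infection, dehiscence, seroma, hematoma, DVT) are largely perioperative, and the device is described as absorbed in 6 to 9 months (2.2, 5.1). This stands and limits the size. However, 7.2 records serious and non-serious events, and 12.4 does not restrict the summary to related or perioperative ones.
- **Other rules might supply a cut-off.** The 7.2 sentence on tracking serious events (30, with no unit, after the last dose) concerns how long such events are tracked, not the period summarised. Censoring of non-completers in 12.4 does not help, because a control who finishes at T5 is a completer.
- **Twelve controls say little anyway.** At a 10% risk the chance of no control event at all is 0.9^12 = 28%. This stands: a common window removes the expected bias but not the imprecision.

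A reader might infer that BioBridge is bound to look two to three times as harmful, or that the safety comparison is made uninterpretable. The documents do not support either. The first needs a constant hazard and ignores chance; the second is owed more to the control arm's size than to the window.

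**Conclusion.** The point holds as a gap in the planned safety summary. The collection schedule differs by arm, the analysis waits for the longer follow-up, and nothing equalises the period summarised. With no device effect, the BioBridge arm can be expected to show a higher percentage of participants with an event whenever events occur after T5.

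The size rests on an assumed rate and timing. At a 12-month risk of 20%, the ratio ranges from 2.4 (constant hazard) through 1.36 (70% of hazard in year 1) to 1.0 (no hazard after year 1). If events are heavily front-loaded the distortion is small and chance may well reverse it.

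It would be wrong to infer that efficacy inference or participant protection is compromised. The volume and skin-thickness analyses use data to month 12. The stopping rule in 7.3 counts BioBridge-related infections alone, and the monitoring committee's review of serious events (7.2, 11.2) does not depend on this summary. The change should be made because it is simple and best settled before the data are seen.

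**What to change.** Add to 12.4, under Analysis Population:

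> Between-arm summaries of adverse events cover surgery to T5 (12 months + 10 days) in both arms. Events after T5 are collected in BioBridge recipients only and are reported in a separate single-arm table without comparison with control.

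Do not substitute a rate per patient-year over unequal follow-up for the common window, for the reason shown in the working.

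The cost is two sentences of analysis-plan wording. No visit, measurement or consent changes, and no safety information is lost, because late BioBridge events are still reported in full.

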12 months. We will conduct the primary analysis to evaluate whether there is a difference between the treatment and control arms in the volume reduction of the affected limb at 12 months. We will fit the linear mixed effects model below assuming an AR(1) covariance structure. We will evaluate the sensitivity of our assumption about the covariance structure by assuming an unstructured covariance in a sensitivity analysis. Let Y_{ij} represent the reduction in volume of the affected limb for subject i at time j (for $j = 3, 6, 9$, and 12 months), γ_i be the random intercept for subject i , ϵ_{ij} be the error for subject i at time j , trt_i be an indicator for whether subject i is in the BioBridge arm, and $m3_{ij}$; $m6_{ij}$; $m9_{ij}$; $m12_{ij}$ be indicators for whether a measurement on subject i at time j was taken at Month 3; 6; 9; or 12, respectively. To assess whether there is a volume reduction of the affected limb at 12 months, we will test the null hypothesis that $\beta_1 + \beta_7 = 0$ vs the alternative hypothesis of $\beta_1 + \beta_7 \neq 0$.

$$Y_{ij} = \beta_0 + \gamma_i + \beta_1 trt_i + \beta_2 * m6_{ij} + \beta_3 * m9_{ij} + \beta_4 * m12_{ij} + \beta_5 * m6_{ij} * trt_i + \beta_6 * m9_{ij} * trt_i + \beta_7 * m12_{ij} * trt_i + \epsilon_{ij}$$

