We will also perform a sensitivity analysis where we only include subjects with complete data who can provide quantitative changes. Such an analysis relies on an assumption that the data are missing completely at random, an assumption that we do not feel is practical in most clinical trial settings and certainly not here. The motivation for performing this analysis; however, allows us to assess how robust our findings are to deviations in our assumptions of missingness. A final sensitivity analysis will be performed where we impute data using multiple imputation techniques that rely on an assumption that the data are NOT missing at random. More specifically, our imputation model will assume those with missing values in the treatment arm are less likely to have a salutary treatment effect. Such sensitivity analyses will provide a context in which we can appropriately interpret the primary findings. In this sensitivity analysis, we will assume a range of volume reductions in the treatment arm (eg, 90%; 75%; 50% of the reduction observed in the control arm). If we find a statistically significant reduction in the treatment arm as compared to the control arm, the range of reductions will be chosen such that the range covers the “tipping point” where the difference in the two arms is no longer statistically significant. This “tipping point” analysis is in place of a worst-case sensitivity analysis because there is not a clearly defined “worst-case” in a non-binary outcome. Our sensitivity analysis will follow the advice given in “Strategy for intention to treat analysis in randomized trials with missing outcome data.”²⁵

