12.6.2 Sample size justification

In order to successfully test the null hypothesis, we have performed sample size calculations. After careful review of the published literature, we are able to identify a study in which the effect of the surgery on limb circumference (as a surrogate for limb volume) has been quantitated and for which a published effect size of 51% reduction in limb volume with standard deviation of 19% is available for standard care.³³ We have utilized this published value (SD = 19%) to calculate our power in relationship to the detectable alternative. If we allow for a 4:1 ratio of VLNT in intervention: control arms, and successful project completion of the protocol by 48 VLNT with BioBridge subjects and 12 controls (VLNT without BioBridge), we have utilized an alpha = 0.05 and a power = 0.9 to predict that the detectable alternative would be \pm 20%.

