12.6.3 Effect size justification

An additional volume reduction of 20% ascribable to the BioBridge (versus VLNT only) would represent a substantial and clinically relevant amelioration in the surgical outcome when compared to current, standard VLNT without BioBridge supplementation. This magnitude of treatment differential has been demonstrated for the BioBridge in lymphedema, both in our published large animal study as well as in pilot observations of the surgical effect of the BioBridge performed in the Dominican Republic (unpublished observations).

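### With 48 v 12 subjects, the month-12 test rests on equal SDs in the two arms and no planned analysis checks this; baseline excess volume is also absent from the model

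*Combined protocol and SAP*

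**What the plan says.** Section 12.4 models the outcome at months 3, 6, 9 and 12 with terms for treatment, month and treatment by month, plus a random intercept: "We will fit the linear mixed effects model below assuming an AR(1) covariance structure". The test is of the treatment difference at month 12, two-sided. No variance parameter carries an arm subscript and no baseline covariate appears.

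Four sensitivity analyses are planned in Section 12.4:
- The covariance pattern is relaxed "by assuming an unstructured covariance in a sensitivity analysis". This is not stated to be by arm.
- Completers are analyzed as treated: "A sensitivity analysis will use the set of subjects enrolled and treatment-assigned in the study who completed the study protocol".
- Complete cases: "We will also perform a sensitivity analysis where we only include subjects with complete data who can provide quantitative changes".
- Multiple imputation under a not-missing-at-random assumption, with a tipping point.

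On estimation, the section says only "Generalized linear mixed effects models are maximum likelihood based methods"; neither REML nor a df method is named. It explains missing at random as meaning "that missingness is related to observed values only such as baseline volume values and treatment arm".

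Sections 3.4 and 12.1.1 set 4:1 allocation. Section 12.6.2 gives the only SD: a "published effect size of 51% reduction in limb volume with standard deviation of 19% is available for standard care". Two other sections bear on spread. Section 2.3 hypothesizes that BioBridge will make results steadier and more predictable than unaided VLNT. Section 5.1 expects a device that fails to leave the outcome as in the control arm. Section 12.5 carries the same methods to caliper thickness.

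**The concern.** With equal arms, unequal SDs do little harm to a pooled test. At 4:1 they matter, because the pooled variance is learned mostly from the large arm while the uncertainty of the difference comes mostly from the small one. If BioBridge outcomes are less variable than control, the standard error is too small: the test rejects too often under equal means, and an interval from the model is too narrow whatever the mean difference. If they are more variable, the standard error is too large and power is lost. The planned analyses vary the pattern over visits, the population or the handling of missing values, so they could all agree with one another and still share this assumption.

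The baseline point is separate and smaller. The plan offers baseline volume as an example of what missingness may depend on, yet the fitted model does not condition on it.

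**Working it through.** **Inputs.** From Sections 12.6.2 and 12.6.3: 48 and 12 subjects, SD 19, alpha 0.05, power 0.9, difference 20 points. The test is two-sided (Section 12.4). I read the modeled outcome as the percentage primary outcome. Every BioBridge SD other than 19 is an assumption.

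**1. The plan's own figure.** SE = 19 × √(1/12 + 1/48) = 6.13. Detectable difference = (1.960 + 1.282) × 6.13 = 19.9; with t on 58 df it is 20.2. Power at 20 points is 0.903 (normal) or 0.894 (t). The stated ±20% is reproduced. It uses one SD for both arms.

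**2. Where the variance comes from.** BioBridge share of the pooled df: 47/58 = 81%. Control share of the variance of the difference at equal SDs: (1/12)/(1/12 + 1/48) = 80%.

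**3. Unequal SDs at month 12.** Control SD is 19 and BioBridge SD is s.
- Pooled SE = √[(11 × 19² + 47 × s²)/58] × √(1/12 + 1/48)
- True SE = √(19²/12 + s²/48)

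For s = 14.25: pooled √233.0 × 0.3227 = 4.93; true √(30.08 + 4.23) = 5.86. Error rates and power come from 400,000 simulated trials per row. The arm-specific test is Welch with Satterthwaite df.

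| s | Pooled SE | True SE | Type I, pooled | Type I, arm-specific | Power at 20, pooled | Power at 20, arm-specific |
|---|---|---|---|---|---|---|
| 28.5 | 8.70 | 6.86 | 0.014 | 0.051 | 0.65 | 0.80 |
| 19 | 6.13 | 6.13 | 0.050 | 0.051 | 0.893 | 0.865 |
| 14.25 | 4.93 | 5.86 | 0.098 | 0.051 | 0.957 | 0.888 |
| 12.67 | 4.55 | 5.78 | 0.121 | 0.051 | 0.969 | 0.893 |
| 9.5 | 3.84 | 5.65 | 0.182 | 0.050 | 0.985 | 0.901 |

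Hand check: 2 × [1 − Φ(1.96 × 4.93/5.86)] is about 0.10, and with 3.84/5.65 about 0.18. If the device only shifts the mean, interval coverage is one minus the type I error, about 90% and 82% in those two rows. The high pooled power in the lower rows is partly bought by the understated SE.

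**4. The four-visit model.** With complete data, an unstructured covariance common to the arms reduces to the pooled month-12 test. In 4,000 simulated trials per case (REML, 58 df, random-intercept share 0.5 and AR(1) 0.5, all assumed), control-to-BioBridge SD ratios of 1, 1.5 and 2 gave:
- random intercept + AR(1): 0.046, 0.116, 0.175
- common unstructured: 0.047, 0.118, 0.179

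So the planned covariance sensitivity analysis does not correct the arm difference. It does correct something else. If the SD grows from 12 to 19 over the visits equally in both arms, AR(1) gives 0.104 and unstructured 0.052. In the same setting, a single arm-specific scale on a constant-variance AR(1) model still gave 0.106 to 0.108, so variances must be free by visit as well as by arm.

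**5. If the device works.** Two illustrations, neither from the documents. If half the patients gain 40 points and half none, SD = √(19² + 20²) = 27.6, and power is 0.67 pooled v 0.81 arm-specific. If values above 100 are piled at 100, pooled coverage is 94.3% (means 71 v 51) or 92.4% (85 v 65).

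**6. Baseline.** Residual SD = 19 × √(1 − r²). For assumed r = 0.3: 18.1, detectable difference 19.0. For r = 0.5: 16.5 and 17.2. For r = 0 there is no gain.

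**The case against.** A reader might infer from the table that this trial's false-positive rate is 0.10 to 0.18. The documents do not support that. Those rates need a device that narrows the spread and leaves the mean unchanged, and no BioBridge SD is given. Section 5.1 expects a failed device to perform like control, and then the SDs are equal and the test is nominal. Section 2.3 states a hypothesis, not data, and couples predictability with better efficacy, so it bears on interval width more than on false positives. This stands and limits the point. What remains is that the only text on spread points toward the direction that shrinks the standard error, and nothing planned would show it.

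Three further objections have weight:
- Section 12.4 specifies a test and no confidence interval. The coverage argument applies only to an interval someone takes from this model.
- The loss is modest in several cases where the device works. The ceiling is not built into the endpoint either, since the formula exceeds 100 when the treated arm ends smaller than the other.
- The arm-specific test has its own cost. With identical, strongly skewed arms (assumed skewness 1 to 2), its type I error was about 0.06 to 0.07, against just under 0.05 pooled. This argues for placing it beside the primary model.

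On baseline, a reader might infer that omitting it biases the primary result. The text names baseline volume only as an example of an observed value, and baseline excess volume is already the denominator of the outcome. The claim is limited to precision, plus conditioning on a variable the plan itself mentions.

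**Conclusion.** The point holds as a cheap improvement, not as a flaw that invalidates the primary analysis. The model has one covariance for both arms and no baseline term. At 48 v 12 its month-12 inference depends on equal SDs, and no planned sensitivity analysis examines that.

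The size cannot be fixed from the documents. It runs from nothing (equal SDs), through a pooled SE at 84% or 68% of its true value (assumed BioBridge SD 14.25 or 9.5), to a valid test that loses about 15 points of power (0.65 v 0.80 at SD 28.5). These figures assume normal outcomes, complete data and a control SD of 19. The sample size statement is correct on its own inputs.

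**What to change.** (a) Add baseline excess volume (mean of S1 and S2) and its interaction with visit to the Section 12.4 equation, and baseline caliper thickness to the secondary model. The data are already collected. The gain depends on an unknown correlation.

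(b) Beside the mixed model, not in place of it, pre-specify one sensitivity analysis of the month-12 contrast with variances that differ by arm and by visit, and Satterthwaite df. Fitting it to all visits, for example as a heterogeneous AR(1) by arm, keeps subjects who lack a month-12 value. A month-12-only Welch-type version drops them.

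(c) State REML and the df method for the primary model. At equal SDs, ML with a normal reference gave 0.059 against 0.049 for REML with 58 df (20,000 trials, assumed random-intercept share and AR(1) both 0.4).

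Cost: SAP wording and one extra model run, with no new data. As a sensitivity analysis, (b) leaves primary power untouched. Its own power at equal SDs is slightly lower (0.89 to about 0.87), and its type I error can reach about 0.06 to 0.07 with strongly skewed outcomes. Because the trial is open-label, these choices should be written down before outcome data are examined.
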